Investigational Medicinal Product	¹¹ C-YJH08 at a dose of up to 20 mCi will be administered. It will be injected intravenously. For cohort A (n = 6), dosimetry calculation will be performed by obtaining whole body (vertex to thighs) PET images up to five time points during 0-90 minutes post injections. For cohort B and C (n=10 each), one time point will be obtained based on the results of cohort A.
Study population	Approximately 26 patients total will be enrolled in one of two following cohorts: Cohort A (N = 6 patients): Patients with any solid tumor malignancy with evidence of one or metastases on conventional imaging. Cohort B (N = 10 patients): Patients with metastatic CRPC will undergo ¹¹ C-YJH08 PET at the time of progression by PCWG3 criteria on systemic therapies (e.g. enzalutamide, apalutamide or darolutamide). Cohort C (N = 10 patients): Patients with any solid tumor malignancies other than prostate adenocarcinoma with one or more metastases on conventional imaging. Enrollment in Cohort B and C will be conducted after completion of enrollment in Cohort A.
Rationale for Study	The proposed patient studies represent the first-ever cancer patient imaging studies with ¹¹ C-YJH08 PET. The patient population for Cohort A is designed to determine the dosimetry of the imaging agent, and will enroll any solid tumor malignancy. The patient population for Cohort B is designed to enrich for GR-overexpressing tumors, by selecting mCRPC patients at the time of progression by PCWG criteria on systemic therapies. And Cohort C is designed to include patients with any solid tumor malignancies other than prostate adenocarcinoma with one or more metastases on conventional imaging. Successful completion of the dosimetry cohort (Cohort A) will provide the necessary preliminary data to support subsequent enrollment in Cohort B and C.
Primary Objectives	
 1. Cohort A: To determine the feasibility of metastatic lesion detection in using ¹¹C-YJH08 PET. 2. Cohort B and C: To determine the mean percent change from baseline at the time of progression on systemic therapy in $SUV_{max-ave}$ on paired ¹¹C-YJH08 PET on a per-patient and per-lesion basis.

Secondary Objectives	
 1. To determine the safety and determine average organ uptake of ¹¹C-YJH08. 2. To descriptively report the patterns of intra-tumoral uptake of ¹¹C-YJH08 on whole-body PET, including by site of disease, uptake by tumor type, inter-tumoral and inter-patient heterogeneity, and tumor-to-background signal. 3. Cohort B and C: To determine whether baseline uptake on ¹¹C-YJH08 PET is associated with subsequent clinical outcomes including objective response rate, progression-free survival, and PSA50 response.
Exploratory Objective	To determine the association between uptake on ¹¹ C-YJH08 PET with GR expression and transcriptional signature scores on paired metastatic tumor biopsies.
Sample size	Approximately 26 patients with various solid tumor malignancies will be enrolled in the two cohorts as outlined above.
Duration of study	Approximately 18-24 months from date of first patient enrolled.
Safety Assessments	Safety monitoring will include adverse event assessment during Screening, 60 minutes (+/- 15 min), and 2 hours (+/- 30 min) and 24 hours (+/- 4 hours) following ¹¹ C-YJH08 injection.
Study Schema	<pre> graph TD A["Safety/Dosimetry Lead-In"] --> B["Cohort A: Any solid tumor malignancy (N = 6)"] A --> C["Cohort B: Metastatic CRPC PD on AR inhibitor (N = 10)"] A --> D["Cohort C: Other solid tumor malignancy (N = 10)"] </pre>

List of Abbreviations

AE	adverse event
ALP	alkaline phosphatase
ALT	alanine aminotransferase
AST	aspartate aminotransferase
BUN	blood urea nitrogen
CBC	complete blood cell (count)
CNS	central nervous system
CR	complete response
CRF	case report form
CT	computerized tomography
CTCAE	Common Terminology Criteria for Adverse Events
CTMS	Clinical Trial Management System
DFS	disease-free survival
DLT	dose limiting toxicity
DSMC	Data and Safety Monitoring Committee
DSMP	Data and Safety Monitoring Plan
ECG/EKG	electrocardiogram
ECOG	Eastern Cooperative Oncology Group
FDA	Food and Drug Administration
FDG	Fluorodeoxyglucose
FLC	free light chain
GCP	Good Clinical Practice
GFR	glomerular filtration rate
HBeAg	hepatitis B "e" antigen
HBV	hepatitis B virus
HCV	hepatitis C virus
HDFCCC	Helen Diller Family Comprehensive Cancer Center
HIPAA	Health Insurance Portability and Accountability Act
HIV	human immunodeficiency virus
ICF	informed consent form
ICH	International Conference on Harmonization
IDS	Investigational Drug Services (UCSF)
IND	investigational new drug application
IP	investigational product

1.1 Background and Rationale

With the widespread clinical implementation of potent and selective inhibitors of the androgen receptor for the treatment of CRPC, there is now an urgent unmet need to define and overcome mechanisms of resistance to these therapies. The landscape of resistance mechanisms to therapies like the AR antagonist Enz is highly complex, with several molecularly discrete mechanisms defined in preclinical models, and no clear understanding as to their relative incidence in patients. Moreover, biological screening to identify which mechanism(s) may have arisen in a given patient is not routine clinical practice, which complicates the development of well-organized clinical studies with experimental therapeutics to determine which resistance pathways are treatable.

[figure not shown]

Figure 1. GR signaling as a mechanism of resistance to standard of care therapies for mCRPC that target AR. **A.** A schema showing how GR overexpression by CRPC cells can bypass the effects of Enz. For example, GR in complex with cortisol can bind to androgen response elements to induce transcription. Moreover, activation of E3 ligases like AMFR can lead to ubiquitin-mediated suppression of 11 β -HSD2, which in turn increases cortisol within CRPC cells. **B.** Structures of three GR antagonists currently in clinical trials to test if GR suppression can extend overall survival in patients with mCRPC and other cancers. The structure of YJH08, the radiotracer we developed to measure GR expression in cells with PET, is also shown. The methyl group colored in red shows the site of radiolabeling with carbon-11.

Appreciating these concerns, several years ago we began developing small molecule radiotracers for PET to identify Enz resistant CRPC lesions that express GR. Our interest in this area stemmed from early preclinical reports showing that GR overexpression in human prostate cancer xenografts was a spontaneous response to chronic Enz treatment, and GR transcriptional activity overcame the antitumor effects of Enz therapy in vitro and in vivo (**Figure 1A**). Since this milestone, numerous manuscripts from other labs have disclosed biological findings supportive and consistent with these data. Moreover, preclinical studies have shown that dual AR/GR antagonists, or selective GR antagonists paired with Enz have antitumor activity (**Figure 1B**). Collectively, these data strongly support a role for GR expression and biology in resistance to anti-androgen therapy, and three ongoing clinical trials are testing the therapeutic potential of overcoming treatment resistant CRPC with GR antagonists more systematically (CORT125281: NCT03437941; ORIC-101: NCT03928314; RU486: NCT02012296).

With the current enthusiasm for GR as a drug target, the timing is ideal to conduct human imaging studies to determine if GR expression in mCRPC can be visualized on PET. Achieving

this goal would empower the community with a crucial companion diagnostic for (1) prospectively identifying patients whose tumors express GR to evade Enz (and therefore may be likely to respond to a GR antagonist), and (2) studying the PD effects of GR antagonists holistically to identify dosing strategies that maximize antitumor effects while minimizing on-target, off tissue effects.

Our studies identified a small molecule radiotracer, termed ^{11}C -YJH08 that specifically binds to GR in rodent models, and has excellent pharmacokinetic properties (**Figure 1B**).

1.2 Pre-Clinical Data

Our first-generation radiotracers targeting GR were derivatives of potent and GR-selective corticosteroids. We made two molecules, termed ^{18}F -GR01 and ^{18}F -GR02, which were both potent and selective for GR in vitro (**Figure 2A**). ^{18}F -GR01 was quickly abandoned due to metabolic instability in vivo. While ^{18}F -GR02 was highly stable in vivo, and specifically bound to GR in normal and prostate cancer tissue, the uptake of ^{18}F -GR02 was very low in prostate cancer tumors compared to virtually all normal tissues, including clinically relevant tissues like the bone (**Figure 2B**). After publishing our findings in *Oncotarget*, we began developing second-generation radiotracers that we expected would have better pharmacokinetics and tissue exposure.

[figure not shown]

Figure 2. First-generation radiotracers developed during the FY14 IDA were suboptimal for prostate cancer detection. **A.** Two steroid-based radiotracers, GR01 and GR02 were potent and selective for GR. However, GR01 was unstable in vivo. **B.** While ^{18}F -GR02 was stable, and the tracer bound GR in tumors, the uptake in prostate cancer was significantly lower than normal tissues and equivalent to bone.

After a focused medicinal chemistry screen, we discovered YJH08, a non-steroidal GR modulator with high affinity for GR ($K_d \sim 0.4$ nM) and at least 100-fold lower affinity for nuclear hormone receptors in the same family (**Table 1**).

To prepare ¹¹C-YJH08, the phenol **1** was alkylated with ¹¹C-methyl iodide (produced by the UCSF cyclotron and radiopharmacy) using chemistry that is applicable to GMP radiotracer synthesis¹¹. The decay corrected yield was ~52% and the radiochemical purity was >99% (**Figure 3**). The specific activity was calculated to be 880 Ci/mmol. Parenthetically, we were also able to prepare ¹⁸F-YJH08. While the yield was sufficiently high for animal and human studies (~12%), and fluorine-18 is more widely available than carbon-11, we opted to pursue ¹¹C-YJH08 for further studies given that the radiochemistry was more adaptable to clinical translation.

Liga nd	GR	AR	PR	MR	GR	AR	PR	MR
Re fere nce	$2.03 \times 10.96 \times 10.27 \times 10.94 \times 10.4$							
YIH08401	$\times 10.20 \times 10.55 \times 10.90 \times 10.7$							

Table 1. In vitro affinity data show that YJH08 is a potent and selective ligand for GR. These data were collected in cells overexpressing the indicated full-length nuclear hormone receptor using a ligand displacement assay. Reference ligands were dexamethasone, DHT, progesterone, estradiol, and eplerenone.

[figure not shown]

Figure 3. Radiosynthesis of ^{11}C -YJH08. A schema showing the conditions for the methylation reaction. This simple radiochemistry was consistently high yielding, and is readily adaptable for human dose preparation.

like thermogenesis. Radiotracer uptake in the bone was low (<0.5% ID/cc), suggesting the radiotracer could be useful for detecting osseous mCRPC. Although radiotracer uptake in the liver was high, liver is not a common site of metastasis for mCRPC adenocarcinoma.

To characterize the biodistribution of ¹¹C-YJH08 in vivo, we first conducted a dynamic PET scan over 60 min in immunocompetent male C57Bl6/J mice. Region of interest analysis was applied to generate time activity curves, which showed that the radiotracer rapidly cleared from serum, as expected. We also observed radiotracer uptake in normal tissues known to harbor high GR expression. For instance, radiotracer uptake in the brain was very high (~2% ID/cc), and ~100 fold higher than what was observed for ¹⁸F-GR02. Moreover, we observed high uptake in supraspinal brown adipose tissue (~4% ID/cc), a tissue in which GR expression is understood to control seminal processes

[figure not shown]

Figure 4. In vivo blocking studies reveal that ^{11}C -YJH08 specifically binds GR in vivo. **A.** Biodistribution data collected 20 min post-injection showing the suppression of ^{11}C -YJH08 uptake in several mouse tissues by dexamethasone (Dex, $n = 5/\text{arm}$). Dex was administered via two routes involving oral gavage of 50 mg/kg for three days prior to radiotracer injection or administration of a water-soluble dexamethasone-cyclodextrin (CD) complex via intraperitoneal injection at 10 mg/kg one hour prior to radiotracer injection. * $P < 0.05$. At right is shown the blocking data observed in the brain. * $P < 0.01$ **B.** The percent changes in radiotracer uptake per tissue among mice exposed to dexamethasone or Dex-CD versus vehicle. **C.** Representative CT and PET/CT images showing the suppression of ^{11}C -YJH08 binding in selected organs in vivo by Dex treatment.

We next performed treatment studies to demonstrate that ^{11}C -YJH08 accumulation in tissues is due to specific GR binding. Wild type C57Bl6/J mice were treated with the synthetic agonist dexamethasone via oral gavage for three days to occupy the ligand binding domain on GR, which in turn suppressed ^{11}C -YJH08 uptake in nearly every normal tissue (Figure 4A). Moreover, ^{11}C -YJH08 uptake in tissues was significantly higher in adrenalectomized mice compared to intact mice, consistent with a GR dependent mechanism of action (Figure 4B). Collectively, these data underscore that ^{11}C -YJH08 binds GR in vivo, and show that ^{11}C -YJH08 can measure GR occupancy by endogenous or synthetic ligands.

We next conducted a pilot study to test if ^{11}C -YJH08 can detect a PC3 tumor in vivo. PC3 tumors embedded in the renal capsule took up very high levels of ^{11}C -YJH08 (Figure 5A). Radiotracer uptake ($\sim 3\%$ ID/g) was significantly higher in the tumor compared to GR rich tissues like the brain and lungs. Moreover, the radiotracer uptake was significantly higher than what was observed in bone, further underscoring the clinical utility of the radioligand. Lastly, digital autoradiography of the affected kidney was applied to define relative uptake of the radiotracer in the tumor and normal kidney parenchyma (Figure 5B and 5C). The radiotracer uptake in the tumor was qualitatively much higher than the level observed in the kidney. These early data suggest that ^{11}C -YJH08 could be a useful tool for measuring GR expression in mCRPC.

The rodent dosimetry was recently performed at UCSF, and the estimated effective dose to an adult human male (73 kg) is 0.0067 mSv/MBq (Table 2). This value shows that the radiotracer is very safe, and a dose of up to 20 mCi per scan is justifiable. Using this funding mechanism, we are also performing single species rodent toxicity studies with Charles River Laboratories.

The radiotracer will be synthesized to GMP standards in the UCSF radiopharmacy, a FDA certified PET drug manufacturer. Anticipated timeline for IND submission is first quarter of 2021.

1.3 Overall Study Rationale

The proposed patient studies represent the first-ever cancer patient imaging studies with ¹¹C-YJH08 PET. The patient population for Cohort A is designed to determine the dosimetry of the imaging agent, and will enroll any solid tumor malignancy. The patient population for Cohort B is designed to enrich for GR-overexpressing tumors, by selecting mCRPC patients at the time of progression by PCWG criteria on systemic therapies. And Cohort C is designed to include patients with any solid tumor malignancies other than prostate adenocarcinoma with one or more metastases on conventional imaging. Successful completion of the feasibility portion of the study (Cohort A) will provide the necessary preliminary data to support subsequent enrollment in Cohort B or C.

[figure not shown]

Figure 5. ^{11}C -YJH08 detects a GR-rich PC3 tumor in the renal capsule. **A.** Ex vivo biodistribution data showing that radiotracer accumulation in the PC3 tumor is higher than the level observed in GR-rich tissues like the brain and lungs. Radiotracer uptake is also higher than the level observed in bone, suggesting the signal to noise in the PET assay may be substantial enough to detect mCRPC. **B.** Digital auto-radiography overlaid with H&E show the high uptake of the radiotracer in the PC3 tumor compared to the normal kidney. **C.** A higher magnification field of view shows the colocalization of high radiotracer uptake with the tumor.

Table 2. A summary of the mouse dosimetry data for (\pm) - ^{11}C -YJH08. The values were calculated from a 90 min dynamic PET acquisition in intact male or female C57Bl6/J mice.

Organ	Absorbed Dose (mGy/MBq) or Equivalent Dose (mSv/MBq)	
	Adult male (73 kg)	Adult female (60 kg)

Adrenals	0.00533 ± 0.000748	0.00578 ± 0.000156
Brain	0.00140 ± 0.000022	0.00229 ± 0.000078
Breasts		0.00286 ± 0.000129
Esophagus	0.00831 ± 0.004249	0.00544 ± 0.000439
Eyes	0.00194 ± 0.000092	0.00223 ± 0.000061
Gallbladder Wall	0.00602 ± 0.000876	0.00459 ± 0.000041
Left colon	0.00374 ± 0.000769	0.00437 ± 0.000314
Small Intestine	0.00325 ± 0.000446	0.00325 ± 0.000114
Stomach Wall	0.01628 ± 0.005962	0.01925 ± 0.002944
Right colon	0.00367 ± 0.000548	0.00339 ± 0.000070
Rectum	0.00249 ± 0.000093	0.00280 ± 0.000087
Heart Wall	0.06753 ± 0.050725	0.02570 ± 0.005677
Kidneys	0.00714 ± 0.000174	0.00785 ± 0.001344
Liver	0.01568 ± 0.001377	0.01863 ± 0.001258
Lungs	0.01350 ± 0.011132	0.00909 ± 0.000339
Pancreas	0.00665 ± 0.002374	0.00545 ± 0.000182
Ovaries		0.00288 ± 0.000090
Prostate	0.00250 ± 0.000105	
Salivary Glands	0.00226 ± 0.000156	0.00241 ± 0.000068
Red Marrow	0.00310 ± 0.000771	0.00289 ± 0.000101
Osteogenic Cells	0.00223 ± 0.000391	0.00217 ± 0.000069
Spleen	0.00378 ± 0.000828	0.00432 ± 0.000300
Testes	0.00204 ± 0.000046	
Thymus	0.01004 ± 0.005999	0.00498 ± 0.000454
Thyroid	0.00355 ± 0.001070	0.00297 ± 0.000118
Urinary Bladder Wall	0.00247 ± 0.000136	0.00288 ± 0.000114
Uterus		0.00284 ± 0.000085
Total Body	0.00355 ± 0.000856	0.00366 ± 0.000121
Effective Dose (mSv/MBq)	0.00673 ± 0.002757	0.00649 ± 0.000433

2 Study Objectives and Hypotheses

2.1 Study Hypotheses

1. **Cohort A:** ^{11}C -YJH08 PET will demonstrate feasibility of uptake within one or more metastatic lesions.
2. **Cohort B and C:** ^{11}C -YJH08 PET will detect metastatic lesions with high sensitivity using conventional imaging as a reference standard.

2.2 Primary Objectives

Primary Objective	Endpoint(s)	Time Frame
1. Cohort A: To determine the feasibility of metastatic lesion detection in using ^{11}C -YJH08 PET.	Cohort A: Sensitivity of metastatic lesion detection in using ^{11}C -YJH08 PET.	2 days
2. Cohort B and C: To determine the mean percent change from baseline at the time of progression on systemic therapy in $\text{SUV}_{\text{max-ave}}$ on paired ^{11}C -YJH08 PET on a per-patient and per-lesion basis.	Cohort B and C: Mean percent change from baseline at the time of progression on systemic therapy in $\text{SUV}_{\text{max-ave}}$ on paired ^{11}C -YJH08 PET on a per-patient and per-lesion basis.	Baseline to time of progression

2.3 Secondary Objectives

Secondary Objective	Endpoint(s)	Time Frame
1. To determine the safety and determine average organ uptake of ¹¹ C-YJH08.	Safety as recorded by CTCAE v 5.0 criteria and organ dosimetry of ¹¹ C-YJH08 PET.	2 days
2. To descriptively report the patterns of intra-tumoral uptake of ¹¹ C-YJH08 on whole body PET, including by site of disease, uptake by tumor type, inter-tumoral and inter-patient heterogeneity, and tumor-to-background signal.	Descriptive patterns of intra-tumoral uptake of ¹¹ C-YJH08 on whole body PET, including by site of disease, uptake by tumor type, inter-tumoral and inter-patient heterogeneity, and tumor-to-background signal will be assessed.	2 days
3. Cohort B and C: To determine whether baseline uptake on ¹¹ C-YJH08 PET is associated with subsequent clinical outcomes including objective response rate, progression-free survival, and PSA50 response.	Association between baseline uptake on ¹¹ C-YJH08 PET with subsequent clinical outcomes including objective response rate, progression-free survival, and PSA50 response	Baseline to time of progression.

2.4 Exploratory Objective

Exploratory Objective	Endpoint(s)
1. To determine the association between uptake on ¹¹ C-YJH08 PET with GR expression and transcriptional signature scores on paired metastatic tumor biopsies	Association between uptake on ¹¹ C-YJH08 PET with GR expression by IHC and transcriptional signature scores on paired metastatic tumor biopsies

3 Study Design

3.1 Characteristics

This is a first-in-human phase 1 imaging study of ¹¹C-YJH08 PET in patients with advanced solid tumor malignancies.

3.2 Number of Subjects

Approximately 26 patients will be enrolled in one of the following cohorts:

Cohort A (N = 6 patients): Patients with any solid tumor malignancy with evidence of one or more metastases on conventional imaging.

Cohort B (N = 10 patients): Patients with metastatic CRPC will undergo ¹¹C-YJH08 PET at the time of progression by PCWG3 criteria on systemic therapies.

Cohort C (N = 10 patients): Patients with any solid tumor malignancies other than prostate adenocarcinoma with one or more metastases on conventional imaging will undergo ¹¹C-YJH08 PET at the time of progression.

Enrollment in Cohort B and C will be conducted after completion of enrollment in Cohort A.

3.3 Eligibility Criteria

Patients must have baseline evaluations performed within 28 days prior to the baseline ¹¹C-YJH08 PET, except for baseline conventional imaging which must be completed 12 weeks prior to and including baseline visit. Patients must meet all inclusion and exclusion criteria. In addition, the patient must be thoroughly informed about all aspects of the study, including the study visit schedule and required evaluations and all regulatory requirements for informed consent. The written informed consent must be obtained from the patient prior to enrollment. Once it has been ascertained that subjects are eligible for the study, their authorization to use personal health information for this study and their informed consent will be obtained. Each subject will be assigned a unique study identification number at the time of study enrollment in order to ensure confidentiality of study data.

3.3.1 Inclusion Criteria

Subjects may be included in the study if they meet all of the following criteria:

1. Disease characteristics by cohort, as defined by:

Cohort A) Histologically-confirmed metastatic solid tumor malignancy.

Cohort B) Metastatic castration-resistant prostate cancer with progression on systemic therapies by PCWG3 criteria.

Cohort C) Metastatic advanced solid tumor malignancy other than prostate adenocarcinoma with at least one metastasis on conventional imaging.

2. The subject is able and willing to comply with study procedures and provide signed and dated informed consent.
3. Eastern Cooperative Oncology Group (ECOG) Performance Status of 0 or 1.
4. Age 18 years or older at the time of study entry
5. Adequate organ function, as defined by:
 - Serum creatinine \leq 1.5 x ULN OR estimated creatinine clearance $>$ 50 ml/min
 - Total bilirubin \leq 1.5 x ULN
 - Hemoglobin \geq 8.0 g/dL
 - Platelet count \geq 50,000/microliter
 - Absolute neutrophil count \geq 1000/microliter

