5.2 Schedule of Procedures and Assessments

5.2.1 Screening Assessments

The screening procedures and assessments must be completed within 28 days of baseline PET (PET/CT or PET/MR) scan except for staging scans which need to be completed 12 weeks prior to baseline PET. All screening procedures may be performed on the same day as baseline PET, provided screening and eligibility confirmation is completed and verified by Principal Investigator prior to initiation of PET.

- Baseline conditions
- Vital signs including heart rate and blood pressure

- Concomitant medication review
- AE assessment
- Demographic information (e.g. age, race, height, weight, and body mass index)
- Staging scans - cross-sectional imaging of the chest/abdomen/pelvis (CT or MRI; with IV contrast if medically permissible) within 12 weeks of baseline ^{11}C -YJH08 PET.
- ECOG or Karnofsky Performance status
- Laboratory procedures
 - Serum creatinine
 - Total bilirubin
 - Aspartate aminotransferase (AST)
 - Alanine aminotransferase (ALT)
 - Complete blood count + differential
 - Prostate-specific antigen (PSA)
 - Serum testosterone. Result may be pending at the time of completion of baseline PET provided documentation of ongoing LHRH analog treatment is available (see eligibility criteria above)

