6.2.5 Serious

An adverse event or suspected adverse reaction is considered *serious* if, in the view of either the investigator or sponsor, it results in any of the following outcomes:

- Death
- Life-threatening adverse event
- Inpatient hospitalization or prolongation of existing hospitalization
- A persistent or significant incapacity or substantial disruption of the ability to conduct normal life function
- Congenital anomaly/birth defect
- Cancer

Important medical events that may not result in death, are life-threatening, or require hospitalization may be considered serious when, based upon appropriate medical judgment, they may jeopardize the patient or subject and may require medical or surgical intervention to prevent one of the outcomes listed in this definition. Examples of such medical events include allergic bronchospasm requiring intensive treatment in an emergency room or at home, blood dyscrasias or convulsions that do not result in inpatient hospitalization, or the development of drug dependency or drug abuse.

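### Cohorts A and C can enrol women, but eligibility, screening and schedule are silent on pregnancy, breastfeeding and childbearing potential

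*Combined protocol and SAP*

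**What the plan says.** Section 3.1 describes the trial: "This is a first-in-human phase 1 imaging study of" the tracer. Section 3.3.1 sets the disease criterion for Cohort A as "Histologically-confirmed metastatic solid tumor malignancy" and for Cohort C as "Metastatic advanced solid tumor malignancy other than prostate adenocarcinoma with at least one metastasis on conventional imaging". Neither is limited by sex. The age criterion, for all cohorts, is "Age 18 years or older at the time of study entry".

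Section 3.3 makes these lists the gate to the study: "Patients must meet all inclusion and exclusion criteria". The six exclusions in 3.3.2 concern capacity to consent, recent systemic glucocorticoids, adrenal insufficiency on replacement, Cushing's disease or syndrome, ability to comply with procedures, and contraindications to MRI (only for patients scheduled for PET/MRI).

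The screening laboratory list in 5.2.1 contains creatinine, bilirubin, AST, ALT, blood count, PSA and testosterone, with no restriction by cohort. For testosterone it says: "Serum testosterone. Result may be pending at the time of completion of baseline PET provided documentation of ongoing LHRH analog treatment is available". It then sends the reader back to the eligibility criteria. The schedule table has one row for PSA and testosterone at screening and none for pregnancy status. For the optional repeat scan at progression in Cohorts B and C, section 5.2.3 lists vital signs and a medication review.

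**The concern.** Two of the three cohorts are open to women, yet the plan never says what happens if a candidate is pregnant, breastfeeding or able to become pregnant. A site that applies the criteria exactly has no ground for declining such a patient and no listed test that would identify a pregnancy.

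What is at stake is exposure of a fetus or a breastfed infant to a tracer not previously used in cancer patients. Cohort A is itself meant to supply the human organ dosimetry, so the human uterine dose is not known when the first women are injected. Section 1.2 presents no reproductive toxicity data; it mentions only single-species rodent toxicity work, described as under way.

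**Working it through.** No sample size, power or error rate is involved, and the plan states no figure to reproduce. The check is a reading of each place where a safeguard could stand, followed by a dose calculation for scale.

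**Places checked**

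| Place | What it covers | Pregnancy, breastfeeding or childbearing potential? |
|---|---|---|
| 3.3.1, five inclusion criteria | Disease, consent, ECOG, age, organ function | Not mentioned |
| 3.3.2, exclusion 1 | Capacity to consent | Not covered |
| 3.3.2, exclusions 2–4 | Glucocorticoid use, adrenal and Cushing's history | Not covered |
| 3.3.2, exclusion 5 | Ability to comply with procedures | Not covered; it is not a general safety exclusion |
| 3.3.2, exclusion 6 | MRI contraindications, PET/MRI patients only | Not named; cannot reach PET/CT patients |
| 5.2.1, screening list | Conditions, vital signs, laboratory tests, staging | No pregnancy test |
| 5.2.2, baseline procedures | Vital signs, adverse events, laboratory tests, ECG | Not mentioned |
| 5.2.3 and schedule table | Repeat scan; all visits | Not mentioned in any row or column |

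The one reproductive item found is "Congenital anomaly/birth defect" in the definition of a serious event in 6.2.5, repeated in Appendix 2. It classifies an outcome and does not control who is injected.

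**Timing.** Screening may precede the baseline scan by up to 28 days, and the repeat injection in Cohort C comes at progression, at no fixed interval. Status recorded at screening therefore need not describe status at either injection, and the plan gives no later step that would establish it.

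**Screening items.** PSA and testosterone are asked of everyone, but 7.7.3 uses PSA response in Cohort B only. (The third secondary objective in 2.3 names PSA50 under Cohorts B and C together.) The LHRH-analog proviso refers to an eligibility criterion, but neither 3.3.1 nor 3.3.2 mentions LHRH analogs.

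**Dose, for scale only**

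- Injected activity (section 4): about 20 mCi; 20 × 37 = 740 MBq.
- Uterus coefficient (Table 2, adult female): "0.00284 ± 0.000085" mGy/MBq; 0.00284 × 740 = 2.10 mGy.
- Effective dose coefficient (Table 2, adult female): 0.00649 mSv/MBq; 0.00649 × 740 = 4.80 mSv.

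These are per injection and extrapolated from mouse scans. CT dose from PET/CT is not stated and is not included.

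**Number of patients.** Cohorts A and C plan 6 + 10 = 16 evaluable patients, or 6 + 12 = 18 with the recruitment allowance in 7.2. Cohort A may be enlarged, so 18 is not a ceiling. The documents do not give the share who are women, or women of childbearing potential.

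**The case against.** A known pregnancy could well come to light. Screening records baseline conditions, and the Principal Investigator must verify eligibility before the scan. Consent pages are not part of the text available for review, so a safeguard there, or in the imaging site's own procedures, cannot be ruled out. This stands to the extent that the plan only leaves enrolment possible; it does not make it certain. It does not close the gap: verification is against criteria that are silent, and a consent-form statement would not be an eligibility criterion.

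Several stronger readings are tempting and are not supported:

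- *The criteria were written for men.* Outside Cohort B they are sex-neutral. Only the screening items (PSA, testosterone, the LHRH proviso) point to prostate cancer, and that an earlier template was reused is an inference. The fault in the criteria is their silence.
- *The plan expects women because Table 2 has a female column and birth defects count as serious.* The column is a mouse extrapolation and the birth-defect item is part of a general definition. The support that holds is the cohort wording, which sets no sex limit.
- *The fetal dose is the sum of two injections, about 4.2 mGy and 9.6 mSv.* The second injection is optional, comes at progression and is not offered in Cohort A; the sum is one fetal exposure only if a single pregnancy spans both. Maternal effective dose is in any case not fetal dose.
- *Nobody reads the scans, because no formal report is made.* Section 5.2.2 has each scan reviewed by a physician within two working days, with pertinent findings passed to the treating provider.

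**Conclusion.** The narrow point holds. Cohorts A and C admit adults of either sex, and nothing in the eligibility criteria, screening list, baseline procedures or schedule addresses pregnancy, breastfeeding or childbearing potential. A pregnant or breastfeeding woman could meet every stated criterion and be injected. This is more than missing detail, because following the stated gate exactly permits the exposure. Cohort B is unaffected.

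The dose figures of about 2.1 mGy (uterus) and 4.8 mSv (effective) per injection are for orientation and do not measure fetal risk. They rest on mouse-derived coefficients and on 740 MBq actually being given; the synopsis gives 20 mCi as an upper limit, section 4 as an approximate dose, and 7.6 allows the injected dose to be adjusted. How many women would be concerned cannot be derived from the documents; the planned size of Cohorts A and C implies that it is small.

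**What to change.** Reconcile 3.3.1, 3.3.2, 5.2.1 and the schedule table with the mixed-sex population of Cohorts A and C. The specific clinical rule is for the sponsor-investigator to set; the protocol should then:

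- state in the eligibility criteria how pregnancy, breastfeeding and childbearing potential are handled;
- state in the screening list and schedule how that status is established for the baseline injection and for the optional repeat injection;
- state which patients the PSA and testosterone tests apply to, consistently with 7.7.3;
- resolve the LHRH-analog cross-reference, which at present leads nowhere.

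The cost is a few lines of text, a protocol amendment (section 8.4 requires PRC and IRB approval) and a routine check in a small number of women. Sample size, endpoints and analysis do not change.
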